#### **4.4. Prohibitions and Restrictions in the study**

Potential patients must be willing to adhere to the following prohibitions and restrictions during the course of the study:

1. Must restrict consumption of caffeinated drinks to 2 per day during the study and refrain from any consumption for at least 12 hours prior to study visits
2. Must refrain from undertaking any strenuous exercise 48 hrs before all Visits
3. Must refrain from alcohol and/or drug substance abuse during the course of the study

#### **4.5. Screen Failures**

Screen failures are defined as participants who consent to participate in the clinical study

but are not subsequently enrolled in the study. A minimal set of screen failure information is required to ensure transparent reporting of screen failure participants to meet the Consolidated Standards of Reporting Trials publishing requirements and to respond to queries from regulatory authorities. Minimal information includes demography, screen failure details, eligibility criteria, and any SAE.

Individuals who do not meet the criteria for participation in this study (screen failure) may be rescreened. Re-screening will be allowed within the screening period of 90 days. Screen failures related to laboratory results will only be considered for re-screening. Rescreened participants should be assigned the same participant number as for the initial screening.

#### 4.6. Stopping Rules

Dosing for a patient will be discontinued for any of the following events:

1. One occurrence of an SAE assessed to be definitely, probably or possibly related to dosing with the study drug.
2. One occurrence of a Grade 4 AE (i.e. life-threatening) assessed to be considered “possibly related” or “probably related” to the study drug
3. One occurrence a Grade 3 rash or higher or acute systemic allergic reaction.
4. Confirmation of any of the study drug discontinuation criteria as described in [Section 8.3](#).
5. Occurrence of any condition that, in the opinion of the Investigator, significantly jeopardizes the wellbeing and safety of the patient and is assessed to be probably related to dosing with the study drug.
6. Clinically significant changes in vital signs or ECGs (such as arrhythmias) assessed to be considered “possibly related” or “probably related” to the study drug (i.e., no alternative explanation likely).
7. Clinically significant changes in the safety laboratory tests assessed to be considered “probably related” to the study drug (i.e., no alternative explanation likely).
8. A subject experiences a breakthrough (defined by quantifiable HBV DNA increase of  $\geq 1 \log_{10}$  HBV DNA copies/mL above LLOQ) the subject should return to the study site for a confirmatory measurement within two weeks, and if virologic breakthrough is confirmed, EYP001a or placebo dosing should be stopped and NA treatment should be continued or modified at the investigator’s discretion.

If two or more patients meet study drug stopping criteria #1, or #3 to #8, recruitment and dosing should be suspended or terminated for the remaining patients, pending the outcome of a DSMC review. The DSMC must review all safety data and provide clearance prior to dosing any additional patients.

If one patient meets study drug stopping criteria #2, recruitment and dosing should be suspended or terminated for the remaining patients, pending the outcome of a DSMC review.

If one patient experiences a Grade 5 common terminology criteria for adverse event (CTCAE) toxicity (based on CTCAE, version 5.0), or if more than 2 patients develop a Grade 3 CTCAE toxicity in the same category, the study will be paused, and safety reports

will be submitted to the DSMC for review and clearance prior to dosing any additional patients.

In other situations, re-initiation of study drug may be considered after consultation with the Medical Monitor.

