**Table 3 Criteria for Determination of AE Relationship to Study Drug**

Unrelated	The event is definitely not associated with the study drug. Other conditions including concurrent illness, progression or expression of the disease state, or reaction to a concurrent medication explain the reported AE.
Unlikely	The temporal association, subject history and/or circumstances are such that the study drug is not likely to have had an association with the observed event. Other conditions including concurrent illness, progression or expression of the disease state, or reaction to a concurrent medication, appear to explain the reported AE.
Possibly Related	The event follows a reasonable temporal sequence from study drug but could have been produced by the subject's clinical state or other therapies administered to the subject.
Probably Related	The event follows a reasonable temporal sequence from the study drug abates upon discontinuation of the study drug and cannot be reasonably explained by known characteristics of the subject's clinical state
Definitely Related	The event follows a reasonable temporal sequence from the study drug abates upon discontinuation or cannot be explained by known characteristics of the subject's clinical state.

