## 8.2. Serious Adverse Events

### 8.2.1. Definition

An SAE (experience) or reaction is any untoward medical occurrence that at any dose:

- results in death
- is life-threatening

NOTE: The term "life-threatening" in the definition of "serious" refers to an event in which the patient was at risk of death at the time of the event; it does not refer to an event which hypothetically might have caused death if it were more severe.

- requires in-patient hospitalization or prolongation of existing hospitalization

NOTE: inpatient hospital admission refers to an overnight stay in a health care facility

- results in persistent or significant disability/incapacity
- is a congenital anomaly/birth defect
- is an important medical event described as an event that may not result in death, be life-threatening, or require hospitalization but may be considered an SAE when, based upon appropriate medical judgment, it may jeopardize the subject and may require medical or surgical intervention to prevent one of the outcomes listed in the definitions for SAEs. Examples of such medical events include allergic bronchospasm requiring intensive treatment in an emergency room or at home, blood dyscrasias or convulsions that do not result in inpatient hospitalization, or the development of drug dependency or drug abuse.

**Hospitalization:** Treatment within or admission to the following facilities will not meet the hospitalization criteria (however, if any other seriousness criteria as specified above are met, the event will be considered an SAE and reported immediately):

- Hospital visit of <24 hours duration (e.g. patient presented to emergency room, but not admitted to ward)
- Hospitalization of subjects to receive study treatment
- Subjects admitted to a hospice or nursing home for elective non-specific, general care or social reasons
- Hospitalization for prescheduled or elective procedures (such as for pain management, disease staging/restaging procedures or protocol specific procedures).

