13.1 Adverse Events

All AEs including will be coded using MedDRA. All AE summaries will be restricted to TEAEs only. Summary tables will include the number of participants (%) experiencing an event and the number of events. Participants will be counted only once for each SOC and PT level (categorical descriptive analysis).

AE and SAE will be analysed taking into account any identified subject with Sars-Cov2 infection during and post-pandemic measures phases. Such an analysis will be operated through the independent Data Monitoring Committee (DMC).

The TEAE summaries will include:

- Overall summary of TEAEs.
 - Number of TEAEs
 - Number of TEAEs with Severity \geq Grade 3 Severe
 - Number of Serious TEAEs
 - Number of Study Drug Related TEAEs (Drug Related: A Possibly, Probably or Definitely related TEAE)
 - Number of Entecavir (ETV) Related TEAEs (Drug Related: A Possibly, Probably or Definitely related TEAE)
 - Number of Tenofovir Disoproxil Fumarate (TDF) Related TEAEs (Drug Related: A Possibly, Probably or Definitely related TEAE)
 - Number of TEAEs leading to study drug withdrawal
- TEAE summary by SOC and PT.
- TEAE summary of serious events by SOC and PT.
- TEAE summary by SOC, PT and Severity.
- TEAE summary by SOC, PT and relationship to study drug.
- TEAE summary by SOC, PT and relationship to ETV.
- TEAE summary by SOC, PT and relationship to TD.
- TEAE summary of events leading to the study drug discontinuation by SOC and PT.

All AEs will be listed and will include verbatim term, PT, SOC, treatment, causality to study drug, ETV and TDF, severity, seriousness, outcome, and action taken with regards to the study drug and AE. Separate listings will be created for SAEs and events leading to study drug withdrawal.

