16. INTERIM AND FINAL ANALYSIS

16.1 Interim Analysis (DSMC Review meeting)

An unscheduled DSMC review meeting of all available unblinded preliminary safety study data will be conducted when any stopping rules (Protocol Section 4.6) are met in two or more patients. All stopping rules will be listed by treatment group.

Two DSMC Review meeting are scheduled:

1. DSMC Safety Review Meeting on all available unblinded preliminary safety study data:
Safety assessment when 40.8% (n=20 out of 49) patients reach week 8 resulting in a decision on continuation of the study based on safety (Go/No go decision); enrolment would remain ongoing during this review.
2. DSMC Safety Review and Futility Analysis Meeting on all available unblinded preliminary virology, safety, PK and PD study data:
Safety and futility when 50% patients (n=25) reached week 12, resulting in a decision on continuation of the study (Go/No go decision) based on safety and evidence of a benefit of EYP001 (HBsAg, other secondary viral markers); enrolment is ongoing during this review.

The DSMC review meeting will be performed on all available primary and secondary endpoints according to the DSMC charter, which describes the overall guidelines, composition, roles, and responsibilities of the independent DSMC for the EYP001-201 study, including the selection of DSMC members, timing of meetings, methods of providing information to and from the DSMC, frequency and format of meetings, data analysis recommendations, and DSMC relationships with other parties participating in the conduct of this study.

The futility assessment will be performed to determine if EYP001 has no benefit at a point when 50% of patients have reached 12 weeks of dosing. The futility assessment will be performed by the DSMC according to the following rules:

- A treatment effect of -1.0 on a log₁₀ scale of HBsAg for the primary endpoint at 16 weeks, and a common standard deviation of 1.08 was assumed and the treatment effect would be -0.5 after 12 weeks of treatment, with common standard deviation of 0.7 Using a one-sided alpha of 0.05 and 80% power (beta = 0.20), a group sequential design, incorporating a futility and efficacy O'Brien-Fleming analysis when 50% of patients have reached 12 weeks of treatment, needs inclusion of 49 patients.
- Table 2 gives the probability of stopping early under the null and alternative hypothesis, at the time of the interim analysis.

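### Stopping criterion 2, the only numbered criterion that suspends the study after one patient, leaves out Grade 4 events rated Definitely Related

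*Protocol*

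**What the plan says.** Protocol Section 4.6 lists eight events that end dosing for a patient and then says how many patients must meet a criterion before the whole study is suspended.

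- **Criterion 1** covers "One occurrence of an SAE assessed to be definitely, probably or possibly related to dosing with the study drug".
- **Criterion 2** covers "One occurrence of a Grade 4 AE (i.e. life-threatening) assessed to be considered" possibly or probably related. The synopsis repeats this.
- **Two-patient rule:** "If two or more patients meet study drug stopping criteria #1, or #3 to #8", recruitment and dosing stop until the DSMC has reviewed the data.
- **One-patient rule:** "If one patient meets study drug stopping criteria #2, recruitment and dosing should be suspended or terminated", again until the DSMC has reviewed.

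Table 3 (Section 8.1.3) grades causality on five levels: Unrelated, Unlikely, Possibly Related, Probably Related and Definitely Related. SAP Section 13.1 treats the top three as drug related: "Number of Study Drug Related TEAEs (Drug Related: A Possibly, Probably or Definitely related TEAE".

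**The concern.** Criterion 2 names two of the three related levels and omits the strongest. Taken as written, a Grade 4 event that the investigator is surest was caused by the drug gets a weaker study-level response than one that is only possibly related. No safety reason for this is given, and none is apparent. Criterion 1, directly above it, names all three levels, which points to an omission in drafting. That is an inference, but a strong one.

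At stake is the mandatory suspension of the study after a single drug-related Grade 4 event. That safeguard should not depend on each reader assuming that probably includes definitely.

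**Working it through.** The documents give no figure to reproduce, so the check is a comparison of wording followed by an enumeration.

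**Step 1. Causality wording of the criteria in Section 4.6.**

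| Criterion | Related levels named | Patients needed to suspend the study |
|---|---|---|
| 1 (SAE) | possibly, probably, definitely | 2 |
| 2 (Grade 4 AE) | possibly, probably | 1 |
| 5 (patient's wellbeing and safety) | probably | 2 |
| 6 (vital signs, ECG) | possibly, probably | 2 |
| 7 (safety laboratory tests) | probably | 2 |
| 3, 4, 8 (rash or allergy; liver rules; virologic breakthrough) | no causality condition | 2 |

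Of the five criteria that use a causality rating, only criterion 1 names the top level. Of the eight criteria, only criterion 2 acts after one patient.

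**Step 2. One Grade 4 event under criteria 1 and 2, read literally.**

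| Rating | Serious: patients needed to suspend | Not serious: patients needed to suspend |
|---|---|---|
| Possibly | 1 (criterion 2) | 1 (criterion 2) |
| Probably | 1 (criterion 2) | 1 (criterion 2) |
| Definitely | 2 (criterion 1) | not triggered by either |

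In the bottom right cell, criteria 3, 4 or 8 may apply to particular events, but they need two patients. Because criteria 5, 6 and 7 also omit definitely, an event outside 3, 4 and 8 would literally meet no numbered criterion.

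**Step 3. Can a Grade 4 event be non-serious?** By definition, yes. Section 8.2.1 limits life-threatening, in the SAE sense, to actual risk of death at the time: "it does not refer to an event which hypothetically might have caused death if it were more severe". Section 1.4.3.3 also reports one Grade 4 ALT/AST increase in earlier experience together with no SAE. That event was interpreted as an HBV flare and is relevant here only to show that grade and seriousness can differ.

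**Step 4. Does another rule restore the one-patient trigger?** None does.

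- The unnumbered one-patient pause in Section 4.6 is for Grade 5 only.
- The Grade 3 pause needs more than two patients with toxicity in the same category.
- The unscheduled DSMC review in SAP Section 16.1 takes place "when any stopping rules (Protocol Section 4.6) are met in two or more patients".

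**Step 5. Is definitely contained in probably?** Not by Table 3. The levels are separate categories. Probably Related requires both that the event abates on stopping drug and that the patient's clinical state does not reasonably explain it. Definitely Related says the event "abates upon discontinuation or cannot be explained by known characteristics of the" patient's clinical state, joined by *or*. An event that has not yet abated can therefore fit the top level without fitting the one below.

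**The case against.** The strongest reply is that nobody would apply the rule this way. A safety officer or DSMC would hardly conclude that stronger causal evidence calls for less caution. Criteria 6 and 7 equate the rating with there being no likely alternative explanation, which suggests that probably was meant as a floor. An event that abates and has no other explanation also satisfies the text of Probably Related. This lowers the practical risk, but the rule still leaves the strongest rating to inference when criterion 1 shows how to name it.

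The non-serious branch is also open to challenge. Criterion 2 and Table 4 describe Grade 4 as life-threatening, and most such events would be reported as SAEs. The earlier ALT/AST case is thin support: under Section 8.1.5 a laboratory change that is not clinically significant might not be recorded as an AE at all. This is fair, and the branch rests mainly on the definition in Section 8.2.1. The serious branch is unaffected: it still needs two patients instead of one.

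The two-patient wording for unscheduled DSMC review is weak evidence of what would happen in practice, because it also passes over criterion 2's own one-patient trigger, and the DSMC charter is not among the documents. That too is fair. The wording shows only that this provision does not fill the gap.

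Finally, individual protection is largely intact. Related SAEs stop the patient's dosing and go to the sponsor within 24 hours, the Section 8.3 liver rules apply through criterion 4 whatever the causality, and Section 4.7 lets the investigator discontinue anyone. This limits the weight of the point but does not answer it.

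**Conclusion.** The concern holds: criterion 2 is wrong as written, and the point is minor. For a Grade 4 event rated definitely related, the number of patients needed to suspend the study rises from one to two if the event is serious; if it is not serious, neither criterion 1 nor criterion 2 is triggered. The fault with consequences is in one criterion of eight. In criteria 5, 6 and 7 the same gap is a matter of consistency, since they need two patients in any case.

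The conclusion assumes a literal reading of Section 4.6 with Table 3's five levels kept distinct. What is lost is only the automatic one-patient suspension. SAP Section 15 records the sponsor's decision of 17 February 2021 to suspend enrolment, so the part that still matters after that date is suspension of dosing for patients on treatment. No estimate, test or error rate is affected.

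**What to change.** Reword criterion 2, in Section 4.6 and in the synopsis, so that it names possibly, probably and definitely related. Add definitely to criteria 5, 6 and 7 in both places.

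The SAP needs no change: Section 16.1 refers to Protocol Section 4.6, and Listing 16.2.9.9 shows rule numbers only. Design, data collection and analysis stay as they are.

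The cost is one word in each of four criteria, in two places. The study already uses protocol clarification letters (SAP Section 21), which would be the simplest route. If the sponsor regards a change to a stopping rule as an amendment, Section 12.1 requires IRB/IEC approval but allows an amendment that reduces risk to participants to take effect first.

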#### **4.7. Participant withdrawal criteria**

Each participant has the right to withdraw from the study at any time. In addition, the Investigator may discontinue a participant from the study at any time if the Investigator considers it necessary for any reason, including the occurrence of an AE or noncompliance with the protocol.

Participants who withdraw from the study for any reason will not be replaced unless it is mutually agreed upon, in writing, by the Investigator, the medical monitor, and Sponsor.

If a participant withdraws or is discontinued from the study, the reason(s) for the discontinuation from the study and primary reason will be recorded. An ET Visit is planned for a follow-up approximately one week after administration of their final last dose of study medication, regardless of how many days the patient was in the study.

If a participant is discontinued from the study with an ongoing AE or an unresolved laboratory result that is significantly outside the reference range, the Investigator will attempt to provide follow-up until a satisfactory clinical resolution of the laboratory result or AE is achieved.

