##### **Safety & Tolerance:**

- **Pruritus:** In an ongoing study EYP001-202, NASH subjects treated during 12 weeks (with EYP001a 100mg BID or 200mg QD or 400mg QD or Placebo tablets) had an overall pruritus frequency of 15/24 (64%) subjects, all mild or moderate episodes, except for three Grade 3. Five pruritus episodes led to early treatment termination. This is in contrast with previous experience in study EYP001-103, in which CHB subjects were treated during 4 weeks with EYP001a capsules, and had mostly mild or moderate pruritus episodes: 1 subject of 7 to 9 (11% to 14%) in each of the EYP001 arms (100 mg, 200 mg and 400 mg QD) but increased to 6 of 9 (67%) subjects treated with 200 mg BID. One subject terminated early because of pruritus.
- **ALT/AST:** In study EYP001-202, two grade 3 cases of isolated transient ALT/AST increases, with no signs of liver impairment, occurred around Day 56 of treatment. No Hy's law cases occurred (no confirmed DILI). The designation by the Primary Investigators (PIs) of the liver enzyme elevations did not consider these as clinically significant, with a variance over time with few outliers, overall not unexpected in the NASH patient population. This compares and is in line with previous phase 1 trials results, where ALT and AST values were within the normal range following EYP001a administration in healthy subjects and in study EYP001-103 after 4 weeks of administration of EYP001a to CHB subjects, 5 subjects had Grade 3 (n=4) or 4 (n=1) ALT/AST increases without signs of liver impairment. The changes were interpreted as hepatic flares or typical of those seen in subjects with underlying chronic viral HBV liver disease.

Taken together, these PK and safety/tolerance preliminary findings in the ongoing NASH and phase 1 trial obtained with the EYP001a tablet formulation do not support the use of the 400mg daily EYP001 dose as a tablet. The reduction to 200mg QD (1x200mg tablet) will generate an exposure similar to previously tested and well tolerated 400mg QD (2x200mg capsules). EYP001a 200mg tablet QD dose can be assessed safely in CHB subjects over the planned 16 week treatment period.

For more details, please refer to IB memorandum dated 16 January 2020 ([IB Memo, 2020](#)).

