### **5.9. Blinding**

Study site personnel, including the Investigator and study team, as well as the study patients, will remain blinded to the treatment assignment throughout the course of the study.

Blinding of study treatment will be managed by the packaging and labelling vendor and should be maintained by the clinical investigative site's pharmacy in accordance with the Pharmacy Manual. In the event of a medical emergency where breaking the blind is required to provide medical care to the patient, the investigator may obtain treatment assignment for that patient.

IWRS should be used as the primary method of breaking the blind. If IWRS cannot be accessed, the investigator should contact the Sponsor medical monitor to break the blind. Treatment assignment should remain blinded unless that knowledge is necessary to guide patient emergency medical care. The investigator is requested to notify the Medical Monitor and Sponsor including the medically compelling justification to unblind a patient's treatment assignment.

Blinding of study treatment is critical to the integrity of this clinical trial and therefore, if a patient's treatment assignment is disclosed to the investigator, the patient will have study treatment discontinued. All patients will be followed until study completion unless consent to do so is specifically withdrawn by the patient.

The Sponsor or designee may independently unblind cases for expedited reporting of SUSARs as required by regulators.

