#### **6.2.4. Early Termination (ET) Visit**

The ET Visit is planned for patients who discontinue early from the study for any reason, for a follow-up approximately one week after administration of their final last dose of any study medication, regardless of how many days the patient was in the study. Please refer [Section 19.1](#) for the collection of data based on the following activities planned for the visit:

- Review and record patient's prior and concomitant medications
- Record patient's body weight
- Calculate BMI
- Perform symptom-directed physical examination
- Perform vital signs (systolic/diastolic BP, heart rate, temperature, respiratory rate)
- Pruritus assessment
- AE monitoring
- Perform clinical laboratory analysis including haematology, serum chemistry panel, coagulation tests and lipid and metabolic profile
- Perform serum pregnancy test (for WOCBP only)
- Perform Dipstick urinalysis for all male and female patients
- Perform 12-Lead ECG
- Sampling for analysis of HBV response markers
- PD biomarker sampling
- Liver fibrosis and inflammation assessment
- Perform Fibroscan VCTE
- PK sampling
- Review returned patient diary
- Collect used/unused study drug and assess compliance

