--------------------------	--------------------------	----------------------	----------------------	------------------------------

Section 14.3.1 and Section 14.3.3.x

Page 1, 3, 5, etc.

Group 1 (N=xx)	Group 2 (N=xx)	Group 3 (N=xx)	Group 4 (N=xx)
n (%) m	n (%) m	n (%) m	n (%) m

Page 2, 4, 6, etc.

Group 5 (N=xx)	Group 6 (N=xx)	Group 7 (N=xx)	Group 8 (N=xx)	Group 9 (N=xx)
n (%) m	n (%) m	n (%) m	n (%) m	n (%) m

- **Names and order of Treatment Groups for Listings**

- EYP001a 200 mg QD + NA daily HBeAg+
- EYP001a 200 mg QD + NA daily HBeAg-
- Placebo HBeAg+
- Placebo HBeAg-

- **Names of visits**

- Screening (Listing only)
- Baseline (Table only)
- Visit 1 = Day 1
- Visit 2 = Week 2
- Visit 3 = Week 4
- Visit 4 = Week 6
- Visit 5 = Week 8
- Visit 6 = Week 10
- Visit 7 = Week 12
- Visit 8 = Week 14
- Visit 9 = Week 16
- Visit 10 = Week 20 (Follow-up Visit 1)
- Visit 11 = Week 28 (Follow-up Visit 2)
- Visit 12 = Week 40 (EOS)
- Early Termination
- Unscheduled (Listing only)

- Column widths and text-wrapping may be altered in final output in order to best present the data.
- Footnotes may be added/amended if required.

Table 14.1.1 Summary of Participant Enrolment and Disposition (ITT Set)

	Group 1 (N=xx)	etc.	Group x (N=xx)
Intention-to-Treat Set	xx (xx.x%)	xx (xx.x%)	xx (xx.x%)
Modified Intention-To-Teat Set	xx (xx.x%)	xx (xx.x%)	xx (xx.x%)
Safety Analysis Set	xx (xx.x%)	xx (xx.x%)	xx (xx.x%)
Pharmacodynamic Analysis Set	xx (xx.x%)	xx (xx.x%)	xx (xx.x%)
Per Protocol Analysis Set	xx (xx.x%)	xx (xx.x%)	xx (xx.x%)
Number of Participants who Completed the Study	xx (xx.x%)	xx (xx.x%)	xx (xx.x%)
Number of Participants who did not Complete the Study	xx (xx.x%)	xx (xx.x%)	xx (xx.x%)
Primary Reason for Non-Completion			
Adverse Event	xx (xx.x%)	xx (xx.x%)	xx (xx.x%)
Death	xx (xx.x%)	xx (xx.x%)	xx (xx.x%)
Protocol Violation	xx (xx.x%)	xx (xx.x%)	xx (xx.x%)
Withdrawal by Subject	xx (xx.x%)	xx (xx.x%)	xx (xx.x%)
Lack of Efficacy	xx (xx.x%)	xx (xx.x%)	xx (xx.x%)
Study Terminated by Sponsor	xx (xx.x%)	xx (xx.x%)	xx (xx.x%)
Non-compliance with Study Drug	xx (xx.x%)	xx (xx.x%)	xx (xx.x%)
Lost to Follow Up	xx (xx.x%)	xx (xx.x%)	xx (xx.x%)
Screen Failure	xx (xx.x%)	xx (xx.x%)	xx (xx.x%)
Other	xx (xx.x%)	xx (xx.x%)	xx (xx.x%)

Source Listing: 16.2.1.1, 16.2.1.2

Percentages are calculated (the denominator used for the calculation) based on the number of participants in the ITT Set in each treatment group (N).

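### The protocol does not separate stopping EYP001a/placebo from leaving the study, so Week 16 and Week 40 HBsAg may be lost and the all-randomised effect overstated

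*Protocol*

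**What the plan says.** **Leaving the study.** Under Protocol 4.7 sites "may discontinue a participant from the study at any time if the Investigator considers it necessary for any reason, including the occurrence of an AE". Non-compliance with the protocol is another ground. Section 6.2.4 adds: "The ET Visit is planned for patients who discontinue early from the study for any reason, for a follow-up approximately one week after administration", counted from the last dose of any study medication. Sections 3.4 and 4.7 and Appendix A footnote 2 agree. The ET visit includes "Sampling for analysis of HBV response markers", and 7.1 offers that sample as the alternative to the follow-up samples.

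**Stopping dosing.** Section 4.6 opens: "Dosing for a patient will be discontinued for any of the following events". It does not mention later scheduled visits. Section 8.3 asks only for follow-up until signs or symptoms resolve.

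**Staying in.** Section 5.9 says that if the investigator learns the assignment, "the patient will have study treatment discontinued". The next sentence reads: "All patients will be followed until study completion unless consent to do so is specifically withdrawn by the patient".

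**The SAP.**
- 3.1 summarises ET and end-of-study assessments separately.
- 3.5 imputes missing HBsAg under missing-at-random (MAR), by treatment, and repeats the analysis without imputation.
- 15 presents this as replacing the protocol's zero-change rule.
- 4.1.2 requires a Week 16 assessment for the mITT set, and the PP set builds on mITT.
- Mock Tables 14.2.3.1 to 14.2.4.2 use patients present at the visit as denominators for loss and responder rates.
- Mock Table 14.1.1 lists adverse event, lack of efficacy and "Non-compliance with Study Drug" among reasons for not completing the study. It has no rows for stopping treatment.

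**The concern.** Adverse events, lack of efficacy and non-compliance are reasons to stop a drug. They are not in themselves reasons to stop measuring HBsAg, and the primary set is all randomised patients. Two sites facing the same Week 6 dosing stop could act differently, one ending participation under 4.7 and the other keeping the patient on the calendar under 5.9, and both could cite the protocol.

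Where the patient leaves, the SAP does not make good the loss. The ET value is not assigned to Week 16 or Week 40. Imputation within arm fills an active-arm leaver mostly from patients still taking the drug. The no-imputation mixed model also relies on MAR. The mITT and PP sets drop anyone without Week 16 data. Responder and loss rates leave the missing patients out of the denominator. All of these can favour EYP001a if its effect fades after stopping.

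**Working it through.** **1. The plan's own figure.** Protocol 11.4.1: effect -1.0, 10% drop-out set to zero change, so -1.0 × 0.9 = -0.9; SD 1.08; one-sided 0.05; 80% power; 3:1. Control n = (1 + 1/3) × (1.645 + 0.842)² × 1.08² / 0.9² = 11.9, rounded to 12, plus 36 active = 48. The plan states 49 (37 + 12), at which t-test power is 79.6%. The sample size reproduces, and it treats leavers as having no effect.

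**2. Overstatement.** Let Δ be the on-drug effect at Week 16, d the fraction of the active arm lost, and r the share of the effect a leaver would still show.
- MAR estimate ≈ Δ
- All-randomised effect = Δ × [(1 − d) + d × r]
- Overstatement = |Δ| × d × (1 − r), at most |Δ| × d

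This takes placebo change as zero (so placebo losses do not matter), no rebound above baseline, and exits unrelated to HBsAg other than through stopping the drug. With Δ = -1.0:

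| d | r = 0 | r = 0.5 |
|---|---|---|
| 10% (planned overall rate, applied to active) | 0.10 | 0.05 |
| 20.8% (5/24, assumed) | 0.21 | 0.10 |

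With Δ = 0 the overstatement is zero.

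The 0.10 is the plan's own gap between -1.0 and -0.9. A simulation supports the bound. It used 37:12, eight visits, effects of -0.5 at Week 12 and -1.0 at Week 16 with SDs 0.7 and 1.08, assumed visit correlation 0.9, stops on active only, and an effect fading 20% to 50% per week off drug. Mean Week 16 differences, all patients measured against leavers missing, were -0.81 against -1.00 and -0.84 against -1.01 at 21% stopping, and -0.86 against -0.95 and -0.94 against -1.03 at 10%.

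**3. Where 20.8% comes from.** Protocol 5.4, on study EYP001-202: "Five pruritus episodes led to early treatment termination", among 24 subjects. If each was a different subject, 5/24 = 20.8%, exact 95% CI 7.1% to 42.2%. Across that interval the bound runs from 0.07 to 0.42.

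**4. Loss by arm.** At an equal 10% rate, 37 × 0.10 = 3.7 active and 12 × 0.10 = 1.2 placebo patients are lost. Active's share is 3.7 / 4.9 = 75.5%, from the 3:1 allocation alone.

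**5. Loss and responder rates.** Take the 10% active HBsAg loss rate in SAP 2.4 as the all-randomised rate: 3.7 of 37. If 20.8% (7.7 patients) are missing and none had HBsAg loss, the observed rate is 3.7 / 29.3 = 12.6%.

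**6. Power.** With lost patients set to zero change, power at 20.8% active loss is 70.2%. If they are measured and on average keep half the effect (assumed), it is 79.3%.

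**The case against.** Section 4.7 is permissive and concerns leaving the study. Nothing in 4.6 or 8.3 sends out a patient who only stops dosing: 8.3 allows for restarting, and in the breakthrough rule of 4.6 NA carries on. The ET visit is timed from the last dose of any study medication, and NA runs to Week 40, so stopping EYP001a alone arguably does not trigger it. The follow-up sentence in 5.9 may be meant only for unblinded patients, in which case there is a gap rather than a contradiction. HBsAg is drawn at ET, and SAP 5.1.1 already lists treatment discontinuation with its reason. These points stand. They show that data may be lost, not that they will be.

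A reader might infer that a dosing stop leads to exit, or that the missing data will fall mainly on active because of the drug. The documents support neither. The Amendment 4 summary calls pruritus a class effect, so a higher rate on active is plausible, but no drop-out rate by arm is given and 3:1 allocation alone produces most of the imbalance in counts. The 5/24 figure counts episodes that ended treatment, not exits. It comes from NASH patients, pools placebo with three dose regimens, and predates the pruritus guidance in 5.8.1. In CHB study EYP001-103 (capsules, 4 weeks) one subject stopped early for pruritus.

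The size is also modest against the noise: the standard error at 37:12 is 1.08 × √(1/37 + 1/12) = 0.36. With no drug effect there is no bias from this source, so it does not create a false positive.

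**Conclusion.** The passages must be reconciled. As written they permit loss of Week 16 and Week 40 HBsAg after a treatment stop, and the SAP's handling can overstate the all-randomised effect. The overstatement is up to about 0.10 log10 at 10% active-arm loss and about 0.21 at an assumed 21%. These are upper bounds. They need the -1.0 effect to be true, every stopper to leave, and the effect to fade fully by Week 16. They are overstatements of the effect in all randomised patients whatever treatment they went on to take, which is the natural reading of the ITT set, although neither document defines an estimand.

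SAP 15 records enrolment suspended after about 25 randomisations, roughly 19 active and 6 placebo. The bound depends on the fraction lost and so does not change, but 21% is then about 4 patients rather than 8. In an exploratory Phase 2a trial this is a cheap improvement, not a must-fix.

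**What to change.** **Protocol.** State in 4.6, 4.7 and 6.2.4 that stopping EYP001a/placebo does not by itself end study participation. Unless consent is withdrawn, HBsAg and HBV DNA are still collected at the planned Weeks 16, 20, 28 and 40, consistent with 5.9. Leave the ET visit and its safety assessments unchanged; restricting it would remove checks for patients who do leave.

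**SAP.** Say that values collected after stopping EYP001a/placebo are used in the ITT primary and key secondary analyses. In Table 14.1.1, show treatment discontinuation separately from study discontinuation, as the 5.1.1 listing already does.

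**Cost.** A clarification letter or short amendment, plus SAP wording. The visits and assays are already scheduled for every patient, and no dose or stopping criterion changes. The estimate may be slightly less favourable, and visits already missed cannot be recovered.
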